## **8.2 STRC SAE Reporting Requirements**

The Safety and Toxicity Review Committee (STRC) is responsible for reviewing SAEs for CCCWFU Institutional studies as outlined in Appendix B. STRC currently requires that all unexpected grade 4 and all grade 5 SAE's on these trials be reported to them for review. This procedure is a part of the CCCWFU Data Safety Monitoring Plan that our institution has on file at the NCI. All CRM staff members assisting a PI in investigating, documenting and reporting an SAE qualifying for STRC reporting are responsible for informing a clinical member of the STRC committee as well as the entire committee via the email notification procedure of the occurrence of an SAE.

## **8.3 WFUHS IRB AE Reporting Requirements**

Any unanticipated problems involving risks to subjects or others and adverse events shall be promptly reported to the IRB, according to institutional policy. Reporting to the IRB is required regardless of the funding source, study sponsor, or whether the event involves an investigational or marketed drug, biologic or device. Reportable events are not limited to physical injury, but include psychological, economic and social harm. Reportable events may arise as a result of drugs, biological agents, devices, procedures or other interventions, or as a result of questionnaires, surveys, observations or other interactions with research subjects.

All members of the research team are responsible for the appropriate reporting to the IRB and other applicable parties of unanticipated problems involving risk to subjects or others. The Principal Investigator, however, is ultimately responsible for ensuring the prompt reporting of unanticipated problems involving risk to subjects or others to the IRB. The Principal Investigator is also responsible for ensuring that all reported unanticipated risks to subjects and others which they receive are reviewed to determine whether the report represents a change in the risks and/or benefits to study participants, and whether any changes in the informed consent, protocol or other study-related documents are required.

Any unanticipated problems involving risks to subjects or others occurring at a site where the

study has been approved by the WFUHS IRB (internal events) must be reported to the WFUHS IRB within 7 calendar days of the investigator or other members of the study team becoming aware of the event.

Any unanticipated problems involving risks to subjects or others occurring at another site conducting the same study that has been approved by the WFUHS IRB (external events) must be reported to the WFUHS IRB within 7 calendar days of the investigator or other members of the study team becoming aware of the event.

Any event, incident, experience, or outcome that alters the risk versus potential benefit of the research and as a result warrants a substantive change in the research protocol or informed consent process/document in order to insure the safety, rights or welfare of research subjects.

## **9.0 STATISTICAL CONSIDERATIONS**

This is a pilot study with the primary goal to be able to determine initial estimates of RR, and secondary goals to determine PFS and OS. Data from this trial will also provide additional data concerning the safety profile of the CPI-613 therapy. The anticipated accrual rates, proposed analyses, and sample size considerations are described below.

### Accrual Rate

We anticipate accruing five patients per year for this protocol. Thus, we anticipate that we will reach the target sample size of 20 patients treated at MTD within four years.

### Proposed Analyses

The analyses for this protocol will be primarily descriptive. With a sample size of 20 treated at MTD, we do not expect to see statistically significant effects for the outcomes of interest, however this data will provide useful preliminary data on the overall safety and efficacy of CPI-613 and provide useful data to predict the variability and likely effect sizes for these outcomes.

For the primary outcome, we will present the proportion (along with a 95% confidence interval) of patients who respond. Response rate (RR) is defined as the combined rate of CR, marrow CR, PR, or SD as described by Cheson, et al. (2006). Response criteria are shown in Appendix G. In addition, we will determine the number of patients who achieve HI, and a reduction in transfusion requirements. For the time-to-event outcomes, we will estimate survival curves for OS and PFS using Kaplan-Meier techniques. In addition, we will estimate the 6 month and 1-year OS and PFS rates for these participants. We will also examine toxicities by looking at each toxicity identified earlier in the protocol by grade.

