## 1.0 BACKGROUND AND STUDY OBJECTIVES

### 1.1 Myelodysplastic Syndrome

Myelodysplastic syndrome (MDS) is a diverse collection of hematological malignancies that involve dysplasia of the stem cells in the bone marrow, resulting in disorderly and ineffective hematopoiesis. The number and quality of blood-forming cells decline irreversibly, further impairing blood production. Patients with MDS often develop severe anemia resulting in susceptibility to infection, bleeding, etc., and require frequent blood transfusions. In most cases, the disease progresses over time and the patient develops cytopenia due to deteriorating bone marrow function. The outlook in MDS is poor, and some patients will progress to Acute Myeloid Leukemia (AML) within a few months. The median survival varies from years to months, depending on the risk level of the disease.

Treatment of MDS is complicated. Although allogeneic bone marrow transplant (BMT) is a potential curative treatment for MDS, a match donor is not always available. Furthermore, most patients with MDS are older and not appropriate candidates for BMT. The prognosis and treatment for MDS vary depending on the patient's International Prognostic Scoring System (IPSS) score (Greenberg et al. 1997). Regardless of risk category, a patient's age and existing comorbidities are also factored into treatment decisions. Patients with a Low/Intermediate-1-Risk score (IPSS 0-1) may live with their disease for a number of years. These patients are primarily treated with low-intensity supportive care, especially red blood cell transfusions, to treat their symptoms and maintain their quality of life. In small subsets of Low/Intermediate-1-Risk MDS patients, hematopoietic cytokines or antithymocyte globulin may reduce transfusion requirements. The drawbacks to these treatments are high failure rates even with improved predictive models, and high cost of cytokines. Patients with higher scores (intermediate-2 and high risk; IPSS  $\geq 1.5$ ) are at higher risk of transformation to AML and many will die from their disease within 1 year of diagnosis. Treatment of these patients is with intensive therapies using hypomethylating agents (decitabine and azacitidine). Unfortunately, these agents induce significant toxicities at therapeutic doses. Furthermore, after relapsing from a hypomethylating agent, there is essentially no effective treatment for this disease. Therefore, additional treatment options for MDS are greatly needed.

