## 3.0 PATIENT ELIGIBILITY CRITERIA

### 3.1 Inclusion Criteria

Patients must meet all of the following inclusion criteria before enrollment:

- A. Histologically or cytologically documented MDS of any risk group that has failed previous therapy. (Therapy failure is defined as patients who have been sufficiently treated with previous agents without response in the opinion of the treating physician, or whose disease has progressed or relapsed while on a hypomethylating agent.)
- B. ECOG Performance Status of  $\leq 3$ .
- C. Men and women 18 years of age or older.
- D. Expected survival  $>2$  months.

- E. Women of child-bearing potential (i.e., women who are pre-menopausal or not surgically sterile) must use accepted contraceptive methods (abstinence, intrauterine device [IUD], oral contraceptive or double barrier device) during the study, and must have a negative serum or urine pregnancy test within 1 week prior to treatment initiation.
- F. Fertile men must practice effective contraceptive methods during the study, unless documentation of infertility exists.
- G. Patients must have fully recovered from the acute, non-hematological, non-infectious toxicities of any prior treatment with cytotoxic drugs, radiotherapy or other anti-cancer modalities. Patients with persisting, non-hematologic, non-infectious toxicities from prior treatment  $\leq$  Grade 2 are eligible, but must be documented as such.
- H. Laboratory values obtained  $\leq$  2 weeks prior to enrollment must demonstrate adequate hepatic function, renal function, and coagulation as defined below:
  - aspartate aminotransferase [AST/SGOT]  $\leq$  3x upper normal limit [UNL]
  - alanine aminotransferase [ALT/SGPT]  $\leq$  3x UNL ( $\leq$  5x UNL if liver metastases present)
  - bilirubin  $\leq$  1.5x UNL
  - serum creatinine  $\leq$  1.5 mg/dL or 133  $\mu$ mol/L
  - Albumin  $\geq$  2.0 g/dL or  $\geq$  20 g/L.
- I. Mentally competent, ability to understand and willingness to sign an IRB-approved written informed consent form.
- J. Have access via central line (e.g., portacath).

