### 5.1.2 Safety Assessment

The safety of CPI-613 will be assessed from the first dose to 1 month after last dose of CPI-613. The assessment will be based on:

- evaluation of symptoms
- vital signs
- ECOG performance status and survival
- clinical chemistry (and renal function utilizing the Cockcroft-Gault formula)
- hematology
- coagulation

The specifics of the safety tests are described in Section 5.2. All safety assessment tests are performed during screening (performed within 2 weeks prior to treatment with CPI-613). Additionally, evaluation of symptoms, vital signs, and survival will be assessed on each treatment day, with results available for review within 24 hours before administration CPI-613. ECOG performance status will be assessed on Day 1 of each course. Clinical chemistry (renal function utilizing the Cockcroft-Gault formula) hematology, and coagulation will be performed on Day 1 of each treatment cycle, with results available for review within 24 hours before administration CPI-613.

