#### List of Adverse Events to be Reported:

Abdominal pain  
Alkaline phosphatase  
ALT (SGPT)  
Anorexia  
AST (SGOT)  
Bilirubin (hyperbilirubinemia)  
Calcium (hypercalcemia, hypocalcemia)  
Creatinine  
Diarrhea  
Flushing  
Hemoglobin (anemia)  
Injection site reaction  
Leukocytes  
Lymphopenia  
Nausea  
Neutrophils (neutropenia)  
Platelets (thrombocytopenia)  
Potassium  
Sodium  
Vomiting

All grade 3, 4, 5 adverse events should be reported on flow sheets and in ORIS regardless of whether they are on this list.

Comprehensive Cancer Center of Wake Forest University (CCCFWU)  
A Pilot Study of CPI-613 in Patients with Myelodysplastic Syndrome Who Have Failed Previous Therapy  
CCCFWU #29113

All AEs are described in the Investigator's Brochure, and all of them are considered "expected".

All Serious Adverse Events (SAEs) which are Possibly, Probably or Definitively Related to CPI-613, and Unexpected are required to be reported to Cornerstone Pharmaceuticals via the provided SAE Reporting Form within 7 days. All completed forms must be sent to [name] at Cornerstone. Cornerstone will submit any applicable SAEs to the FDA.

SAE reports must be submitted to Cornerstone by fax or email to the following address:

Department of Regulatory and Clinical Affairs  
Cornerstone Pharmaceuticals, Inc.  
[name]  
[name]  
[contact]  
Telefax: [contact]  
Email: [[contact]](mailto:[contact])

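### Section 9.0 tabulates toxicities by grade without baseline grade or attribution, so cytopenias present at entry may be counted in the toxicity table

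*Combined protocol and SAP*

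**What the plan says.** Safety is a secondary outcome (Section 2.2), and Section 9.0 states its purpose: "Data from this trial will also provide additional data concerning the safety profile of the CPI-613 therapy". The method follows under Proposed Analyses: "We will also examine toxicities by looking at each toxicity identified earlier in the protocol by grade".

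The toxicities meant are those in the Section 8.1 list, which includes hemoglobin, leukocytes, lymphopenia, neutrophils and platelets. Below the list is a wider capture rule: "All grade 3, 4, 5 adverse events should be reported on flow sheets and in ORIS regardless of whether they are on this list". It makes no exception for conditions already present at entry.

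Section 5.1.2 sets the window: "The safety of CPI-613 will be assessed from the first dose to 1 month after last dose of CPI-613". Nothing in the available text limits events to those that are new or worse than before treatment.

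The protocol does define five attribution categories (Section 8.1). It also calls for hematology at screening and before dosing on Day 1 of each cycle (Table 5-1, Section 5.1.2).

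**The concern.** In this disease, low blood counts are part of the condition being treated. Section 1.1 says so: "Patients with MDS often develop severe anemia resulting in susceptibility to infection, bleeding, etc., and require frequent blood transfusions". A table of on-treatment grades therefore mixes two things: how severe the cytopenia was at entry, and what happened after dosing began. With one arm there is no control group against which to set the first, so the patient's own baseline is the only internal reference.

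The plan uses that reference for efficacy. Transfusion frequency is compared with the 8 weeks before enrollment, and hematologic improvement is judged against pretreatment counts. The safety sentence does not use it.

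At stake is whether a reader of the hematologic rows can tell a marrow effect of CPI-613 from the case mix of the patients enrolled. A smaller version of the problem affects other terms, because inclusion criterion G also admits "Patients with persisting, non-hematologic, non-infectious toxicities from prior treatment" up to Grade 2. That criterion concerns non-hematologic toxicity and is not evidence about cytopenias.

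**Working it through.** **The plan's own figure.** Section 9.0 gives no figure for safety. Its only computed figure is the 0.22 maximum distance for the response-rate interval. It reproduces as a normal-approximation half-width at a rate of 0.5: 1.96 × √(0.25/20) = 0.219. This point does not depend on it.

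**What the text establishes**

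1. *Terms.* The Section 8.1 list has 20 entries, of which 5 are blood counts (5/20 = 25%).
2. *Entry.* The laboratory limits in Section 3.1 H cover transaminases, bilirubin, creatinine and albumin. Neither Section 3.1 nor Section 3.2 sets a minimum hemoglobin, neutrophil or platelet count.
3. *Expected baseline.* Section 1.1 describes severe anemia and cytopenia arising from the disease. Table 4 in Appendix H provides for pretreatment hemoglobin below 11 g/dL, neutrophils below 1.0 × 10⁹/L, and platelets below 100 × 10⁹/L, including patients starting below 20 × 10⁹/L. The documents do not single out lymphopenia as a feature of MDS.
4. *Analysis rule.* Section 9.0 says by grade. It does not mention baseline grade, a new-or-worse rule, attribution, or how several records from one patient reduce to one entry.

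Items 1 to 4 together leave room for an unchanged entry cytopenia to be counted.

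**Illustration of size.** The documents give no baseline grade distribution, so the inputs other than n are assumptions:

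- n = 20 (Section 6.1);
- b = share entering with at least one Grade 3 or higher cytopenia that persists and is logged, assumed 30% to 70%, with 20% and 80% as a wider check;
- t = share of the remaining patients who newly reach Grade 3 or higher, assumed 0 or 10%.

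By-grade table: n × [b + (1 − b) × t]. New Grade 3 or higher cases: n × (1 − b) × t, among n × (1 − b) patients who could have one.

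| b | By-grade, t = 0 | New, t = 0 | By-grade, t = 10% | New, t = 10% |
|---|---|---|---|---|
| 20% | 4 of 20 | 0 of 16 | 5.6 of 20 | 1.6 of 16 |
| 30% | 6 of 20 | 0 of 14 | 7.4 of 20 | 1.4 of 14 |
| 70% | 14 of 20 | 0 of 6 | 14.6 of 20 | 0.6 of 6 |
| 80% | 16 of 20 | 0 of 4 | 16.4 of 20 | 0.4 of 4 |

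Worked line: b = 30%, t = 10% gives 20 × (0.3 + 0.7 × 0.1) = 20 × 0.37 = 7.4, of which 20 × 0.7 × 0.1 = 1.4 are new.

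Across the 30% to 70% range, the by-grade count moves by 8 patients (14 − 6) through b alone. Raising t from 0 to 10% moves it by only 1.4 (b = 30%) or 0.6 (b = 70%). Under these assumptions the count mainly reports who was enrolled.

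The denominators here are for new Grade 3 or higher cases. A full new-or-worse count would also include a move from Grade 3 to Grade 4, so its denominator is the number of patients not already at the highest non-fatal grade for that term.

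**The case against.** The strongest reply is that silence is not a rule. A reader might infer that entry cytopenias will be labelled CPI-613 toxicity. No section says that. Section 8.1 provides attribution categories down to unrelated, Section 6.2 ties its dose rules to relatedness, and screening hematology is taken, so an analyst could make the separation. The available text of the adverse event log (Appendix C) shows only header fields and footnotes, so whether it records attribution or baseline status per event cannot be judged. This stands, and it limits the point to *may be counted*. It does not remove the gap: collecting attribution is not the same as planning to use it, and Section 9.0 does not say that it will be used.

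A reader might also infer that this sentence alone stops the trial from showing whether CPI-613 harms the marrow. That goes too far. Hematologic improvement and change in transfusion frequency already compare marrow function with entry, though they measure benefit or transfusion need rather than toxicity. Much of the difficulty also comes from the single arm. Section 1.1 expects cytopenia to develop as the disease progresses, so even a baseline-referenced table mixes drug effect with progression. This stands as a limit on what the fix can deliver.

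The illustrative counts are the assumed share multiplied by 20. This also stands: they show direction and possible scale, and confidence intervals around them would add no information. Nor would 0 of 20 be a fair comparator, since some patients may already be at the grade ceiling.

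Finally, this is a descriptive pilot and no decision rule uses the toxicity table. That limits the consequence. It also means that the descriptive table is itself the safety result and needs to be interpretable.

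**Conclusion.** The point holds in limited form. Section 9.0 does not tabulate toxicities against baseline grade or by attribution, and nothing elsewhere in the available text supplies the rule. With five blood-count terms, no blood-count floor at entry and a disease expected to cause cytopenia, cytopenias present at entry may be counted, and the hematologic rows cannot be read as change on CPI-613.

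The size is unknown. The figure of 6 to 14 of 20 with no new or worsened case rests on three assumptions: that 30% to 70% enter with a Grade 3 or higher cytopenia, that it persists, and that unchanged values are logged as events. The documents do not support saying that entry cytopenias *will* be attributed to CPI-613, or that the trial can say nothing about marrow toxicity. What they support is a cheap improvement to a secondary, descriptive analysis. The sample size, the primary outcome and the 0.22 precision statement are unaffected.

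**What to change.** Replace the toxicity sentence in Section 9.0 with a rule on these lines:

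- For each patient and listed term, cross-tabulate baseline grade against the worst grade from first dose to 1 month after last dose.
- Define baseline as the last value before the first dose, from screening or Cycle 1 Day 1 laboratory tests, together with toxicities documented under Section 3.1 G.
- Count patients, not log entries, with an event that is new or worse than baseline. Use as denominator the patients who could still worsen on that term.
- Show all-cause events and at least possibly related events separately.
- State that, without a control arm, the table cannot separate drug effect from disease progression.

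The cost is a wording change and one extra table, with no new visits, samples or patients. Some data work may be needed. The Pre-Study form (Appendix G) has no field for blood counts or baseline toxicity grade, and the forms schedule in Section 10.0 lists no baseline laboratory form, so existing baseline values may have to be abstracted from the record.

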### Sample Size Considerations

Since this is a pilot study we do not anticipate having statistical power to detect specific effects. However with the sample size of 20, we will be able to estimate the response rate using a 2-sided 95% confidence interval with an interval that will extend no more than 0.22 from the observed response rate.

## **10.0 Data Management and Reporting Schedule**

Tumor response will be assessed based on RR, PFS, and OS (as described by Cheson et al. 2006), as well

Comprehensive Cancer Center of Wake Forest University (CCCFWFU)  
A Pilot Study of CPI-613 in Patients with Myelodysplastic Syndrome Who Have Failed Previous Therapy  
CCCFWFU #29113

as changes in the frequency of transfusion from baseline.

RR and PFS, derived from hematology and bone marrow exam, will be assessed at the following specified time points:

- Baseline (hematology and bone marrow)
- Hematology: week 4 of every 2 treatment cycles until cycle 6 and then every 3 treatment cycles thereafter (i.e., cycle 9, cycle 12, cycle 15, etc) until evidence of disease progression.
- Bone marrow week 4 of cycles 3 and 6, and then at the discretion of the physician or if peripheral blood criteria for a complete remission are met (ie ANC>1000, Platelets >100k and freedom from blood transfusions) thereafter until disease progression

Bone marrow exam results should be documented at each specified time point using the data collection form in Appendix E, and then input into the corresponding REDCap database.

Transfusion frequency should be documented at each specified time point using the data collection form in Appendix F, and then input into the corresponding REDCap database.

Response form (Appendix I) should be completed for each specified time point.

	Data Collection Forms	Due By	Database
Pre-Study / Registration	Signed Consent Registration Form	At time of registration At time of registration	ORIS ORIS
On-Study	Adverse event log (Appendix C) Withdrawal of participation form (Appendix D) Bone marrow exam form (Appendix E) Transfusion data form (Appendix F) Response form (Appendix I)	Within one week Within one week Within one week Within one week Within one week	ORIS REDCap REDCap REDCap REDCap

## Appendix A – REGISTRATION GUIDELINES AND FORMS

The following guidelines have been developed in order to ensure timely registration of your patient.

All patients entered on any CCCFWU trial, whether treatment, companion, or cancer control trial, **must** be linked to a protocol in EPIC within 24 hours of Informed Consent. Patients **must** be registered prior to the initiation of treatment.

In order to ensure prompt registration of your patient, please:

1. Complete the Eligibility Checklist (attached)
2. Complete the Protocol Registration Form (attached)
3. Alert the WFUHS registrar by phone, *and then* send the signed Informed Consent Form, Eligibility Checklist and Protocol Registration Form to the registrar, either by fax or e-mail.

Contact Information:

Protocol Registrar [contact]

Protocol Registrar [contact]

Protocol Registrar E-MAIL ([[contact]](mailto:[contact]))

(\*Protocol Registration is open from 8:30 AM - 4:00 PM, Monday-Friday.)

4. Please fax/e-mail ALL eligibility source documents with registration. Patients **will not** be registered without all required supporting documents.

**Note:** If labs were performed at an outside institution, please provide a printout of the results. Please ensure that the most recent lab values are sent.

Comprehensive Cancer Center of Wake Forest University (CCCWFU)  
A Pilot Study of CPI-613 in Patients with Myelodysplastic Syndrome Who Have Failed Previous Therapy  
CCCWFU #29113

CCCWFU # 29113

